### Falling risk

The Berg Balance Scale is used to determine the risk of falling. The BBS detects deficits at both activity and body function levels. It consists of 14 items. Scaling takes place from 0 points (not possible) to 4 points (independently possible). This results in a total score of 56 points. The individual items are shown in the template in the appendix.

Very good intertester reliability was found in a study of 112 stroke patients (Mao, Hsueh, Tang, Sheu, & Hsieh, 2002).

The best values in terms of validity resulted from the combination of the BBS with the walking speed. This gave a specificity of 70% and 91% sensitivity (Schädler, et al., 2012).

### 8.2.1 Recording of the primary target

The walking speed is tested one day before the first IB or GB and one day after the last IB / GB. So a training effect that could falsify the result should be avoided. It is measured by a physiotherapist.

### 8.2.2 Recording secondary target

The risk of falling is tested one day before the first IB or GB and one day after the last IB / GB. So a training effect that could falsify the result should be avoided. It is measured by a physiotherapist.

## **8.2.3 Recording safety targets**

### **8.2.3.1 Serious Adverse Event (SAE)**

A SAE would be a fall of the patient. If this has happened, a fall protocol will be created on the RehaClinic intranet. It records how the fall came about and under what circumstances, when the fall took place, and which people were present. The patient is examined by the ward physician and, where appropriate, measures for further examination or treatment are initiated. If the patient later describes the fall, as unobserved, the same procedure nevertheless takes place.

### **8.2.3.2 Laboratory**

For the study itself, no laboratory parameters have to be taken. They are supervised as part of the rehabilitation stay. These are mainly blood samples. See visit plan.

### **8.2.3.3 Vitality parameters**

Blood pressure and pulse are measured at least once daily. Also several times daily measurements are possible, depending on the regulation. It is measured by the caregiver. The patient sits during the measurement.

The body temperature is monitored by an ear thermometer only after extra prescription.

Body weight is checked at least twice a week. This can also be prescribed more often, if appropriate comorbidities cause this..

## **8.2.4 Investigations in case of premature termination of studies**

In the event of premature termination of the study which was not caused by normal termination of the stay, a new medical examination will be carried out according to the initial examination. At the discretion of the physician, additional examinations may be arranged.

## **8.3 Study measures during the visits**

### **8.3.1 Visit 1 or screening Visit**

The first doctor contact takes place on the day of arrival. The inclusion and exclusion criteria are examined by file review and, if necessary, by taking anamnesis and testing. The examination complies with the standard of an initial medical examination with anamnesis, inspection, palpation and complete neurological status. If necessary, special tests such as coordination and reflexes are performed.

### **8.3.2 Visit 2 until 8 (see visitation plan)**

At each visit the condition of the patient is inquired. If abnormalities show up, further examinations such as clinical examination, ECG, EEG, X-ray, blood sample, stool sample, etc. will be available. causes. In addition, he is asked how he is doing with the study participation.

### **8.3.3 final visitation**

During the final visit, the patient's condition is also inquired and whether he is satisfied with the participation in the study. For the last medical examination, an overall examination is again carried out as for the initial visit. This takes place according to the standard at the end of the rehabilitation stay.

## **9 SAFETY**

Further details on the security messages can be found in the SOPs of the sponsor.

According to KlinV, SAEs are recorded throughout the study, documented in full and in a standardized manner in the source data and the test sheet, and comprehensively clarified, in which a causal relationship with the investigated intervention can not be ruled out.

The duration of the study starts with the signing of the participant's consent and ends with the last protocol-specific activity, including the safety follow-up examinations.

### **9.1 Definition Serious Adverse Event (SAE)**

#### **Adverse Event (AE)**

An AE is any adverse medical event that occurs in a patient or participant in a clinical trial following a health-related intervention and that is not necessarily causally related to that intervention.

An adverse event (AE) may therefore be any adverse or unintentional reaction (including an abnormal laboratory finding), any symptom or disease associated with the intervention, whether causally related to the investigational medicinal product or not. An AE may also be the onset of a new disease, the worsening of a pre-existing disease, or the recurrence of an episodic disease; These may be multiple or individual complaints or symptoms.

#### **Serious Adverse Event (SAE)**

A SAE is any event that:

- requires inpatient treatment or its extension not provided for in the research plan;
- leads to permanent or severe disability or disability;
- is life threatening or leads to death; or
- results in a congenital anomaly or birth defect.

### **9.2 Documentation / Assessment of Serious Adverse Events**

The investigator has the responsibility to identify, document and determine the causal relationship to intervention.

All SAEs are fully documented on the corresponding SAE page in the CRF. For each SAE, the investigator indicates the beginning, duration, required treatment and outcome of the SAE, as well as changes in the implementation of the intervention.

The causal relationship of the (S) AE with the study intervention is determined by the investigator according to the following definitions:

No correlation	
 
• The event did not begin in any temporal context with the study measure and
 
• The event can be clearly explained by the underlying disease or other factors.
 

Possible correlation	
 
• The event did not begin in any temporal context with the study measure and
 
• The event can not be explained clearly by the underlying disease or other factors.
 

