### 9.3 Report of Serious Adverse Events

If SAEs occur during the conduct of a clinical trial of participating individuals in Switzerland that can not be ruled out to be due to the intervention being studied, the investigator must report these events::

- If the responsible investigator and sponsor examiner are not the same person: to the sponsor within 24 hours of becoming aware, and
  - the responsible EC within 15 calendar days.

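### The causality table in section 9.2 has no category for an event that begins in temporal context with training, and sections 8.2.3.1 and 9.1 disagree on whether every fall is an SAE

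*Combined protocol and SAP*

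**What the plan says.** **Causality.** Section 9.2 makes the investigator responsible for the causal assessment of each (S)AE and gives two categories for it. In both rows the first condition is "The event did not begin in any temporal context with the study measure and". For *No correlation*, the second condition is that the underlying disease or other factors clearly explain the event. For *Possible correlation* it is "The event can not be explained clearly by the underlying disease or other factors". There is no third category and no default.

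**Reporting.** Section 9 covers SAEs "in which a causal relationship with the investigated intervention can not be ruled out". Section 9.3 requires a report for SAEs "that can not be ruled out to be due to the intervention being studied", including to "the responsible EC within 15 calendar days". Neither section refers to the table. Section 9.2 also states: "All SAEs are fully documented on the corresponding SAE page in the CRF".

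**Falls.** Section 8.2.3.1 says "A SAE would be a fall of the patient". No severity or outcome is attached. For each fall, "a fall protocol will be created on the RehaClinic intranet", and the ward physician examines the patient. Section 9.1 defines an SAE by four outcomes: unplanned or prolonged inpatient treatment, lasting or severe disability, threat to life or death, and congenital anomaly. Falls are not named there, and no sentence links the two sections.

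**The concern.** An event that starts during or shortly after the intervention is the kind a causality assessment most needs to classify. Here that is an event during balance training, which under section 7.5.1 includes standing with closed eyes and on unstable surfaces. As worded, the table excludes exactly these events, and it does not match the reporting trigger in sections 9 and 9.3.

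The fall wording decides four things:

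- which falls go on the SAE page of the CRF (section 9.2);
- which falls come under the 15-day report if a causal link cannot be excluded (section 9.3);
- how many SAEs the annual safety report states;
- whether later follow-up is recorded in the CRF or only in the source data (section 9.4).

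Section 10.3.3, headed as the safety analysis, does not settle which definition is counted. Its only sentence is about training the physiotherapists.

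Little else in the plan would catch inconsistent classification. The trial is open (6.5). The investigator normally delivers the training (3.2), assigns causality (9.2) and analyses the data (10.3.2), and independent monitoring is not organised (12.3). The pilot is also meant to prepare a larger trial (4.1), so these definitions could be carried forward.

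**Working it through.** The plan gives no figure to reproduce, so the check is a comparison of the texts.

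**Step 1. The causality table.** Each event has two attributes: whether it began in temporal context with the study measure, and whether it is clearly explained by other factors. That makes 2 × 2 = 4 combinations. Three wordings were tried:

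- A: the current text.
- B: the current text with the *not* removed from the temporal condition of the *Possible* row, which is the obvious one-word repair.
- C: *No* kept as it is, and *Possible* defined as its complement (temporal context present, or not clearly explained).

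| Temporal context | Clearly explained | A | B | C |
|---|---|---|---|---|
| no | yes | No | No | No |
| no | no | Possible | none | Possible |
| yes | yes | none | none | Possible |
| yes | no | none | Possible | Possible |
| **Without a category** | | **2 of 4** | **2 of 4** | **0 of 4** |

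Under A, the two uncovered rows are all the events with temporal context. Under B, the gap moves but stays the same size. Under C, every combination has exactly one category.

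**Step 2. Fit with the reporting trigger.** Sections 9 and 9.3 act on events whose relation to the intervention cannot be excluded. An event with temporal context and no clear other explanation meets that trigger on an ordinary reading, yet has no category under A. Under C it is *Possible*, so table and trigger agree.

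**Step 3. The two SAE definitions.** Take a fall and ask whether one of the four section 9.1 outcomes is present.

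| Section 9.1 outcome present | SAE under 8.2.3.1 | SAE under 9.1 |
|---|---|---|
| yes | yes | yes |
| no | yes | no |

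Let F be the number of falls, Fs the falls with a section 9.1 outcome, and E the other events that meet section 9.1. The SAE count is E + F if every fall counts, and E + Fs if section 9.1 alone applies. The difference is (E + F) − (E + Fs) = F − Fs, the number of falls without a listed outcome.

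**Step 4. Can F − Fs be given a value?** No. The plan states no fall rate for the trial. The cited 39% (section 3) and 46% in the first six months after stroke (section 3.1) come from other studies. Neither is a rate over the three to four weeks of participation (section 6.1), and neither separates falls by outcome. With 20 planned patients, F − Fs could be zero, and even one or two such falls would visibly change the count.

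**The case against.** **The consequences are limited.** The reporting duty does not depend on the table, all SAEs are documented and listed whatever their causality, and every fall is recorded and examined. Nothing in section 10 uses the causality label, so no estimate or sample-size step changes. All of this stands, and it limits the severity.

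**The fall wording may be an addition.** Section 9.1 does not say that *only* its four outcomes count, so section 8.2.3.1 could be read as a trial-specific extension under which every fall is an SAE. That reading is possible, but it is not stated. Section 9.1 is headed as the definition, so the exclusive reading is at least as natural.

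**The section 9.4 effect is thin.** It concerns SAEs still ongoing when a participant leaves the trial, and a fall without a serious outcome would seldom be one. This is the weakest of the listed consequences.

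**The repeated line may be a copying or translation slip, and section 9 refers to sponsor SOPs for further detail.** Both may be true. But section 9.2 says its own definitions decide causality, so the current wording governs. The SOPs and the CRF page are not in the documents, so what happens in practice cannot be judged.

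**The complement wording may label too much as possible.** Training takes place twice a week for three weeks, and temporal context is undefined. Under a broad definition, many otherwise explained events would become *Possible*. This stands as a caution: the term has to be defined along with the rewording.

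**Conclusion.** Both points hold. In section 9.2, two of the four combinations have no category, and these are all the events that begin in temporal context with training. This follows from the wording alone and needs no assumption. The investigator has no valid entry for such an event, and the table does not match the reporting trigger.

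Sections 8.2.3.1 and 9.1 classify a fall without a serious outcome differently, and nothing links them. The SAE count differs by the number of such falls, which is unknown and possibly zero. This point assumes that section 9.1 is a complete definition, which its heading suggests. On the additive reading, what remains is a missing linking sentence.

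Neither defect stops reporting, detection or examination, and neither touches the walking-speed outcome. Both should be corrected before the safety data are classified and before the definitions are reused in a larger trial.

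**What to change.** 1. Reword the two rows in section 9.2 so that they are distinct, exhaustive and consistent with section 9.3. One wording that does this keeps *No correlation* as it stands and defines *Possible correlation* as temporal context present, or no clear explanation by the underlying disease or other factors. Removing the second *not* alone is not enough.
2. State what counts as temporal context.
3. Reconcile sections 8.2.3.1 and 9.1 so that one definition governs the CRF, the reporting and the annual safety report. The sponsor has to decide which; this review does not choose.
4. Optionally, tabulate all falls by arm from the fall protocols, so that the safety description does not depend on the definition chosen.

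The cost is one table row, a short definition, one reconciled sentence and, if wanted, one descriptive table from records already required. The drawback of the example wording is that some events that are otherwise explained but linked in time to training would be labelled *Possible*. How many depends on item 2.

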### 9.3 Report of Serious Adverse Events

If SAEs occur during the conduct of a clinical trial of participating individuals in Switzerland that can not be ruled out to be due to the intervention being studied, the investigator must report these events::

- If the responsible investigator and sponsor examiner are not the same person: to the sponsor within 24 hours of becoming aware, and
  - the responsible EC within 15 calendar days.

#### **Safety and protective measures**

If prompt safety and protection measures are to be taken while conducting a clinical trial, the investigator shall notify these measures and the circumstances in which they became necessary to the EC within 7 days.

#### **Annual safety report**

The investigator submits an annual safety report to the Competent Ethics Committee.

All SAEs are summarily listed in the annual safety report to the Ethics Committee, with the following contents:

- A short, critical summary, taking into account the safety aspects;
- In the cover letter to the annual safety report, the status of the clinical trial in Switzerland should be briefly summarized (number of centers open / closed, number of patients recruited / completed, number of SAEs).

### 9.4 Tracking Serious Adverse Events

Participants terminating the clinical trial (regular or premature) because of

- reported, ongoing SAE, or
- sustained SAE, e.g. laboratory values or alarming vital signs,

are examined during a follow-up visit. This visit will take place until 30 days after completion of the study treatment phase. Information from this follow-up visit will be recorded in the CRF.

Follow-up visits may also be necessary at the discretion of the investigator, even if the subject does not suffer from SAE at the end of the experiment. The information of such visits must be documented only in the source data (e.g., medical records), not in the CRF..

## **10 STATISTICS**

One aim of this pilot study is to determine an appropriate number of cases. Therefore, with the obtained data set using G \* Power Ver. 3.1.9.2 the SampleSize is calculated.

Further descriptive statistics are done with SPSS version 25. The mean values for each assessment are calculated. The absolute and relative frequencies are calculated. To determine the scattering parameters, the standard deviation is determined.

To determine if there is a difference between intervention and control group, first the odds ratio is shown.

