## **5 TARGETS OF THE STUDY**

### **5.1 Primary target**

Improving walking speed by 18 cm/sec would be a successful outcome (Fulk et al, 2011). Whether there is a difference between individual balance training and group balance training is to be determined. To be able to cross a pedestrian traffic light, a walking speed of 1.0-1.2 m/sec would be necessary (Hüter-Becker, et al., 2005). This would be the ideal value.

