## **6 DESIGN AND EXPIRATION OF THE STUDY**

### **6.1 General design and justification of the design**

A controlled, randomized, open pilot study with parallel group design will be conducted.

In each case, ten patients are recruited randomly into the intervention group or control group. It does not pay attention to gender distribution. Each patient takes about three to four weeks to participate in the study. There are three weeks of intervention time.

The screening begins with the registration of the patient, because then usually already a preliminary discharge report, or referral report exists. On the day of arrival the medical admission takes place and the screening is checked. On the second day the Investigator visit the patient and explain to him about the possible participation in the study. He receives the consent form with the explanations from me and is informed that he will answer further questions, e.g. for medical safety to the attending physician could turn. With the signed consent, the randomization and accordingly the planning of the therapies, including initial and reassessment. Depending on the day of arrival, the intervention may begin in the first or second week. With the allocation, the therapists will also be informed, since they are not allowed to do any additional balance training in the therapy. When the sixth balance training is done, the reassessment takes place the next day.

This is an ongoing process for each patient.

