## **6.4 Randomization**

The randomization was prepared and the sealed envelopes numbered in order. Randomization was done using a list randomizer (<https://www.random.org/lists/>). The list is not publicly available.

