### **10.2 Sample size calculation**

It is planned to recruit 20 patients to RehaClinic Kilchberg. This results in 10 patients each for the experimental group and the control group. This number is based more on the temporal than on the statistical factor. It serves only for the descriptive statistics in order to be able to make already first assumptions and to be able to carry out a SampleSize calculation. If this number is not reached by the end of April, the pilot study will nevertheless end. This should ensure the writing of the master thesis, so that it can be delivered on time.

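### No baseline-adjusted arm comparison of walking speed is specified, although baseline speed is measured in every patient and its chance imbalance and spread affect the pilot's effect size and follow-up sample size

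*Combined protocol and SAP*

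**What the plan says.** **Measurement.** Section 8.2.1 sets two measurements of the primary outcome: "The walking speed is tested one day before the first IB or GB and one day after the last IB / GB". The schedule in 8.1 agrees, so a paired baseline value is planned for every patient.

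**Allocation.** Section 6.1 states "In each case, ten patients are recruited randomly into the intervention group or control group" and adds "It does not pay attention to gender distribution". Section 6.4 states "Randomization was done using a list randomizer". No stratum or minimisation factor is named. Eligibility (7.1.1) sets no lower or upper limit on walking speed.

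**Analysis.** Section 10 states "The mean values for each assessment are calculated", followed by frequencies, standard deviations and an odds ratio between the arms whose event is not defined. Section 10.3.2 says only who will do the analysis and when. No covariate, change score, adjusted difference or pre-post correlation appears anywhere.

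**Purpose.** The synopsis, 4.1, 10 and 10.2 make the sample size of a later trial a main product of the pilot. Section 5.1 gives the only stated size of meaningful change: "Improving walking speed by 18 cm/sec would be a successful outcome".

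**The concern.** The best single predictor of a patient's walking speed after three weeks is likely to be the walking speed beforehand. The plan collects it and does not say how it enters the arm comparison. Ten patients per arm are too few for randomisation to be relied on to balance a variable that eligibility leaves wide open.

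Two results of the pilot depend on this. The first is the difference between individual and group training, which a chance difference in starting speed could distort by an amount that depends on the measure compared. The second is the SD entered into G*Power. An SD of end values, of change scores and of baseline-adjusted residuals can give quite different follow-up sizes, and the plan does not say which will be used.

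**Working it through.** **The plan's own figure.** Section 10.2: "This results in 10 patients each for the experimental group and the control group". 2 × 10 = 20 reproduces. No alpha, power, SD or between-arm difference is given, and the section says "This number is based more on the temporal than on the statistical factor", so nothing further can be reproduced.

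**Inputs.** From the documents: 10 per arm; 0.18 m/s as a yardstick (5.1, an improvement benchmark). Assumed, because the documents do not give them: baseline SD 0.15 to 0.50 m/s; pre-post correlation r from 0.5 to 0.9; equal SD at both times; for the follow-up, a between-arm difference of 0.18 m/s, 80% power and two-sided 5%.

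**Step 1: chance baseline gap.** SE = SD × √(1/10 + 1/10) = 0.447 × SD. The chance that the gap exceeds 0.18 m/s in either direction is 2 × [1 − Φ(0.18/SE)].

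| Assumed SD (m/s) | SE (m/s) | Chance of gap above 0.18 m/s |
|---|---|---|
| 0.15 | 0.067 | 0.7% |
| 0.20 | 0.089 | 4% |
| 0.25 | 0.112 | 11% |
| 0.30 | 0.134 | 18% |
| 0.40 | 0.179 | 31% |
| 0.50 | 0.224 | 42% |

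A gap of 0.18 m/s lies inside the central 95% chance range once the SD exceeds 0.18/(1.96 × 0.447) = 0.205 m/s. Section 10.4 excludes patients with incomplete data. If that left 8 per arm, the chance at SD 0.30 would rise from 18% to 23%.

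**Step 2: what a gap does to the comparison.** With equal SDs the slope of end speed on baseline speed is r. With no treatment effect, a baseline gap g gives these expected arm differences:
- end means: r × g. For g = 0.18 m/s this is 0.5 × 18 = 9 cm/s to 0.9 × 18 = 16 cm/s.
- change scores: −(1 − r) × g, that is −0.5 × 18 = −9 cm/s to −0.1 × 18 = −2 cm/s.
- ANCOVA (end speed regressed on arm and baseline): 0, if the relation is linear with the same slope in both arms.

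**Step 3: size of the follow-up.** Variances are SD² for end values, 2(1 − r)SD² for change scores and (1 − r²)SD² for ANCOVA residuals. With SD 0.4 m/s and the noncentral t distribution, n per arm is:

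| r | End values (raw SD) | Change scores | ANCOVA |
|---|---|---|---|
| 0.6 | 79 | 63 | 51 |
| 0.8 | 79 | 32 | 29 |
| 0.9 | 79 | 17 | 16 |

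Multiplying by the variance factor gives the same ANCOVA figures: 79 × (1 − 0.64) = 28.4, rounded up to 29, at r = 0.8.

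**Step 4: precision of r from 20 patients.** By Fisher's transformation, an observed r of 0.8 has a 95% interval of about 0.55 to 0.92 (SE 1/√17). At SD 0.4 the ANCOVA size then runs from about 55 down to 14 per arm.

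**The case against.** **The goals imply change from baseline.** The question, primary goal, target and hypotheses (synopsis, 4.2, 5.1, 10.1) all speak of improvement. If improvement is what is compared, the raw gap is subtracted out and the residual shift is 2 to 9 cm/s, not 9 to 16. At high correlation ANCOVA then saves little: 29 against 32 per arm at r = 0.8. This stands. A reader might infer that the plan ignores baseline altogether; the documents do not support that. They leave its use unspecified, since section 10 never turns improvement into a defined change score.

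**18 cm/s is not a between-arm target.** This also stands. A reader might infer that a chance gap could equal the effect the trial is built to find. Section 5.1 gives 18 cm/s as a success threshold for improvement and leaves the difference between arms open. It is used above only as a yardstick and, for the follow-up, as an assumption.

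**The SD is unknown.** At 0.15 m/s such a gap would be rare (0.7%). Only a range can be given.

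**Raw SDs may never be used.** A reader might infer that the follow-up will be sized on end-value SDs. Section 10 says only that G*Power will be applied to the data obtained, and its reference to each assessment may simply mean each test instrument. The 79 per arm is therefore conditional.

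**It is a descriptive pilot.** No confirmatory conclusion rests on the comparison, and chance imbalance under randomisation is imprecision rather than systematic bias. That limits the seriousness, but the descriptive effect size and SD are the inputs to the next trial.

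**The baseline may be measured after allocation is known.** Section 8.1 draws the envelope on the consent day and tests the next day, and 6.5 rules out blinding. The value still precedes training and can serve as a covariate, but the order should be settled.

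**Conclusion.** The point holds as a gap in specification. Baseline walking speed is planned for every patient, allocation is unstratified with 10 per arm, and no baseline-adjusted comparison is named. It does not show that the plan's comparison is biased or that the follow-up will be oversized.

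The size depends on an SD and a correlation that the documents do not give. A baseline gap above 0.18 m/s ranges from very unlikely to quite likely over SDs of 0.15 to 0.50 m/s. Its effect is large on end means and smaller, with opposite sign, on change scores. For the follow-up, most of the saving at high correlation comes from using baseline at all; the further gain of ANCOVA over change scores is 12 per arm at r = 0.6, 3 at 0.8 and 1 at 0.9 (SD 0.4 m/s). For a pilot, this is a worthwhile, low-cost improvement to the figures it is meant to hand on.

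**What to change.** 1. In 10.3.2, state that reassessment walking speed is compared between arms by linear regression with arm and baseline walking speed as terms, and that the adjusted difference in m/s is reported with its 95% confidence interval. Do the same for the Berg Balance Scale.
2. Report the SDs at both times, the residual SD, and the pre-post correlation with its confidence interval.
3. Base the follow-up size on the residual SD, or equivalently on the raw-SD sample size multiplied by (1 − r²), but not both, since that would apply the reduction twice. Show the result over the confidence interval of r, because a single value from 20 patients could leave the follow-up underpowered.
4. Take the baseline test before the envelope is opened, as the order of steps in the synopsis time plan suggests, and bring 6.1, 7.3 and 8.1 into line. Knowledge of the allocation then cannot affect the covariate.

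Cost: one degree of freedom out of 18, a paragraph in section 10 and a few lines of analysis in SPSS, which the plan already uses. No new data are needed. Step 4 changes only the order of two steps already planned.
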